- 1) To establish the feasibility of completing the quick renal MRI compared to the DMSA scan (using DMSA as the 'gold standard') among children with suspected urinary tract infections (UTI). Children admitted to the American Family Children's Hospital for suspected acute pyelonephritis will undergo a clinical DMSA renal scan and quick renal MRI.
- 2) To establish the sensitivity and specificity of the quick renal MRI compared to the DMSA scan (using DMSA as the 'gold standard') in the diagnosis of renal scars among children with recurrent UTI. Children with recurrent UTI will undergo a clinical DMSA renal scan and quick renal MRI. The sensitivity and specificity of the quick renal MRI to detect renal scars will be determined using DMSA as the standard.

RESEARCH DESIGN AND METHODS

Design and Methods

If study criteria are met for Aim 1, patients will be enrolled during their hospital stay and undergo both a quick renal MRI and a standard of care DMSA scan before discharge. During the patients hospital stay, they will be offered the chance to participate. The PI, a hospital, and/or [name] will be available to recruit and onboard patients. If the patient chooses to do so, they will be consented, and the DMSA and Quick MRI will be schedule to occur within one week of consent, either before or after they are discharged.

If the criteria are met for Aim 2, a DMSA scan will be recommended according to the CDC's Spina Bifida Registry protocol. Patients are also allowed to participate in Aim 2 if they've completed a DMSA scan within the past 6 months. Patients will also be invited to participate in the study by undergoing a quick renal MRI. Spina bifida patients will be identified as qualified for the study ahead of time by the research staff, and will be asked if they would like to participate at their next regularly scheduled clinic visit. If they do choose to participate, they will then be scheduled to receive the DMSA and Quick MRI within 6 months.

For aim 1 patients, there is no specific order for the scans, but both imaging tests should be performed within one week of each other. For Aim 2, there is no specific order for the scans, but they should be performed within six months of each other.

Neither group of patients would experience a delay in receiving antibiotics because it is standard of care.

Patient enrollment and the success of participants completing both studies will be evaluated every 2 months.

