If the recruitment rate is less than 50% of that planned to be completed by 6 months into the study, we will be prepared to expand recruitment to pediatric patients at St. Mary's Hospital.

To enroll additional patients likely to have renal scarring we will contact families of children with spina bifida who have already had a DMSA performed in the past year and invite them to participate. We believe that the quick, non-invasive nature of the test and the accommodated scheduling will appeal to potential subjects. The hospitalist faculty staff are enthusiastic for the development of the quick MRI and are likely to be early adopters of the quick renal MRI; this will facilitate enrollment for Aim 1.

Likewise, for Aim 2, [name] understands that many of her patients are engaged in spina bifida advocacy and will be motivated to participate in a study that promises to ease their lifelong burden of frequent invasive testing.

Quick MRI Imaging: MRI of the kidneys will be performed using a 1.5-Tesla magnet (Signa, GE Medical Systems Milwaukee, Wisconsin, USA). For pyelonephritis, axial diffusion weighted imaging sequences will be used (3 mins if respiratory triggered, 15 secs if patient can hold breath). For renal scar, coronal and axial T1-weighted fat-saturated sequences will be used (10 mins). Below are the specific sequences of the Quick MRI abdomen without contrast for all study patients. Particular sequences were selected based on prior case reports of their accuracy in diagnosing either pyelonephritis or renal scars. All 5 sequences will be done because it will be important to distinguish acute infection from scarring, as well as renal anatomy.

Sequence	Pyelonephritis	Renal scars					
Coronal and axial T1 FAT		Х					
Axial T1 FAT		Х					
Axial DWI	X						
Coronal T2 SSFSE	Gives detail of re	Gives detail of renal collecting system					
Coronal T1 LAVA-Flex	Gives detail of re	Gives detail of renal vasculature					

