All patients must be willing to undergo the Quck MRI and, depending on which aim, the DMSA scan in order to be included.

Exclusion Criteria

For Aim 1: Patients will be excluded from the study of patients with acute pyelonephritis if they do not have evidence of pyuria on their UA, if their urine culture is negative, or are not comfortable having a quick MRI completed.

For both Aims: Patients with contraindications to MRI will be excluded from eligibility (implanted devices such as pacemakers, implanted cardioverter defibrillators, or cochlear implants or if they are or are planning to become pregnant).

Data Collection, Handling, Storage

Subjects' confidentiality will be addressed in multiple ways. There will be a retrospective and prospective review of the data. Data from eligible patients' medical records will be entered into an Excel document. All study records will be kept in secure locations. All data will be maintained only on Department of Urology password- and firewall-protected computers, and on the Department of Orthopedics/Rehabilitation and Urology;s secured network server. Data will not be stored on laptops, notebooks, or other portable computers. The PI has a locked office in a security restricted building (Medical Foundation Centennial Building). Only team members will have access to the data. Data about study subjects will not be shared with anyone other than team members.

The study team will do the following things to ensure the privacy of research participants and confidentiality of data:

- use codes so that no direct subject identifiers are recorded on data collection sheets
- create codes for data that are not based on subject identifiers (i.e., avoid codes that include subject initials or are based on birth dates)
- store the links to the code and code separately from each other
- keep identifiable data in locked cabinets or drawers in rooms with restricted access and/or on password-protected computers housed in rooms with restricted access or housed on departmental servers with limited, password-protected access
- limit the number of participating site team members with access to directly identifiable information

After imaging scans are performed, only DMSA scans will be accessible to the providers via Healthlink. Data/images will be analyzed by [name], and [name] and appropriate radiology staff. Results of data analysis will be passed to research coordinator in order to document findings.

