Study records will be kept for a minimum of 7 years, per campus policy.

Timeline of Activities

Following IRB approval, patient enrollment and completion of imaging studies for both specific aims will occur over 18 months.

	July	August	September	October	November	December	January	February	March	April	May	June	July	August
Enrollment	_													
Team			V			V			V			V		
Meeting			Α						Α			^		
Data														
Analysis &														→
Manuscript														

DATA AND SAFETY MONITORING PLAN

All research related activities will be approved by the institutional review board ensuring that the benefits of participating in this research will outweigh the risks. Overall, although we do not expect any

PI: [name]

problems to occur, care will be taken to ensure complete privacy of the patient, sanitary conditions, patient safety and quality care.

The research assistant in the Department of Urology, will be responsible for the monitoring of this data, under supervision from the PI, [name]. We plan to assess our data and do a primary study evaluation when our enrollment has reached 25% of our stated enrollment goal. Unanticipated problems, adverse events, protocol deviations and violations will be reported to the IRB within 14 days following.

If, at the point of initial evaluation (25% of targeted enrollment), any of the following circumstances occur, the study will be formally stopped for evaluation and possible discontinuation:

- A higher than expected rate of complications in either study arm
- Arm 1:
 - A lack of efficacy of the Quick MRI to accurately diagnosis acute pyelonephritis
- Arm 2:
 - A lack of efficacy of the Quick MRI to accurately image renal scarring

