We will include our initial study evaluation (at 25% of targeted enrollment) in the soonest following continuing review. In the case that our evaluation shows negative results and occurs prior to a continuing review, we will contact the IRB with the information and seek to reevaluate or possible discontinue the study. All study team members have completed relevant training materials, are well versed in maintaining clinical integrity and data validity, and will be formally instructed in the proper application of this protocol. Data/images will be evaluated by the PI, [name], and [name], a study team member. This data will be passed to the research coordinator, whereupon it will be stored securely as outlined in the Data and Record Keeping section of our protocol. The primary data handlers, [name] and the research coordinator, meet every two weeks and can discuss and evaluate protocol adherence, data integrity, and validity as needed during these meetings.

STATISTICAL CONSIDERATIONS

Aim 1 will determine the sensitivity of quick MRI in the diagnosis of suspected acute pyelonephritis in children with febrile UTI. With a power of at least 80%, a target significance level of 0.05, and an estimate of 90% prevalence of DMSA confirmed acute pyelonephritis among children admitted for febrile UTI, the minimum sample size required to detect a change in sensitivity from 80%-90% is 34 subjects.

Aim 2 will determine the sensitivity and specificity of quick MRI in the diagnosis of renal scars in children with spina bifida and recurrent UTIs. With a power of at least 80%, a target significance level of 0.05, and an estimate of 30% prevalence of DMSA confirmed renal scars in this patient group, the minimum sample size required to detect a change in sensitivity from 60-90% and a change in specificity from 70-90% would require a minimum sample size of 64 subjects.

The sensitivity will be calculated with TP/TP+FN. The specificity will be calculated with TN/TN+FP

This is a pilot study and we are trying to get a baseline understanding of the accuracy of Quick MRI. If the preliminary sensitivity/specificity percentages are less than 60%, we would be less enthusiastic about carrying out future research on this question, and vice versa.

REFERENCES

- 1. Freedman, A. L.: Urologic diseases in North America Project: trends in resource utilization for urinary tract infections in children. J Urol, **173**: 949, 2005

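### Nothing requires the quick MRI to be read without knowledge of the DMSA result, so the accuracy estimates could be biased upward

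*Combined protocol and SAP*

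**What the plan says.** Two sentences describe who looks at the images. Data Collection, Handling, Storage says "Data/images will be analyzed by [name], and [name] and appropriate radiology staff". The Data and Safety Monitoring Plan says "Data/images will be evaluated by the PI, [name], and [name], a study team member". Names have been removed from both, but neither sentence divides the work between MRI and DMSA. No section mentions blinding, masking, independent reading, separate readers or an order of reading.

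There is one access rule, in the data-handling section: "After imaging scans are performed, only DMSA scans will be accessible to the providers via Healthlink". The coding rules in the same section are listed as privacy measures for data sheets.

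Design and Methods fixes no scan order for either aim. It admits Aim 2 children who have "completed a DMSA scan within the past 6 months", and to find more children with scarring it approaches families "who have already had a DMSA performed in the past year and invite them to participate".

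Statistical Considerations plans sensitivity for both aims and specificity for Aim 2 only. It names 60% as the level below which interest in further research would fall.

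**The concern.** DMSA is the reference, so every error in the accuracy tables is an MRI reading that disagrees with it. A reader who knows the DMSA result may settle a doubtful MRI the same way. In a DMSA-positive child this turns a false negative into a true positive. In a DMSA-negative child it turns a false positive into a true negative. Both shifts favour the MRI, so Aim 2 sensitivity and specificity and Aim 1 sensitivity could all rise together. A confidence interval would not reveal this, because it covers sampling error only, and enrolling more children would not remove it.

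The plan can be followed to the letter with the MRI reader knowing the answer. At stake is the purpose of the pilot: a baseline for accuracy, and preliminary data for a multi-center study. The same readings feed the evaluation at 25% of enrolment, where, on a lack of efficacy among other triggers, "any of the following circumstances occur, the study will be formally stopped for evaluation and possible discontinuation".

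**Working it through.** **1. What could keep DMSA from the MRI reader**

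- *Reader assignment.* Both sentences treat data and images as one pool, so they provide no separation.
- *Access rule.* It stops the MRI reaching providers through Healthlink. It leaves DMSA open, so it does not act in the direction that matters here.
- *Coding.* It keeps identifiers off data sheets and says nothing about image readers.
- *Timing.* For Aim 2 children who enter with an earlier DMSA, the reference result exists before the MRI is done. Their number is not given.

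**2. The plan's own Aim 2 figure**

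Inputs from Statistical Considerations: sensitivity 60% against 90%, specificity 70% against 90%, level 0.05, power at least 80%, scar prevalence 30%. The plan names no test. A one-sample exact binomial test (two-sided 0.05, so upper tail at most 0.025) gives:

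- Sensitivity: 19 DMSA-positive children, success at 16 or more (tail 0.023, power 0.885). 19 / 0.30 = 63.3, rounded up to 64.
- Specificity: 31 DMSA-negative children. 31 / 0.70 = 44.3, rounded up to 45.

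The larger is 64, which matches the plan. Aim 1's 34 subjects are taken as stated; whether that number follows from its inputs is a separate question.

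**3. Weight of one reading**

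- Aim 2 DMSA-positive: 64 × 0.30 = 19.2, about 19. One reading moves sensitivity by 1/19 = 5.3 points.
- Aim 2 DMSA-negative: 64 × 0.70 = 44.8, about 45. One reading moves specificity by 1/45 = 2.2 points.
- Aim 1 DMSA-positive: 34 × 0.90 = 30.6, about 31. One reading moves sensitivity by 1/31 = 3.2 points.

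**4. Range under an assumption**

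The document gives no size for the bias. Suppose a fraction f of the MRI readings that disagree with DMSA is changed to agree. This f is an assumption and combines how often DMSA is known with how much it sways the reader. Then

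apparent accuracy = true accuracy + f × (1 − true accuracy).

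Columns 2 to 5 start from true values of 60% (sensitivity) and 70% (specificity) and use the exact cut-offs for 19 and 45 children. The last column starts from a true sensitivity of 50% and asks how often it reaches the 60% mark (12 of 19).

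| f | Apparent sensitivity | Chance of at least 16/19 | Apparent specificity | Chance of at least 38/45 | True 50%: chance of at least 12/19 |
|---|---|---|---|---|---|
| 0 | 60% | 2.3% | 70% | 2.1% | 18% |
| 10% | 64% | 4.9% | 73% | 5.4% | 32% |
| 25% | 70% | 13.3% | 77.5% | 17.5% | 58% |
| 50% | 80% | 45.5% | 85% | 63.9% | 92% |

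The direction is always upward. Which row applies, if any, is unknown.

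**The case against.** The best reply is that silence about masking is not evidence of unmasked reading. Radiology staff take part, a radiology co-investigator is listed, and the study may already read the MRI first. That stands, and it limits the point to what the plan allows. Several stronger readings are tempting, and the document does not support them.

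- *That the PI reads the MRI knowing DMSA.* The sentence naming the PI sits beside the 25% evaluation and does not say which test the PI reads. The recruitment sentence, "The PI, a hospital, and/or [name] will be available to recruit and onboard patients", belongs to Aim 1, where that paragraph has consent come before both scans are scheduled. Inclusion Criteria also speaks of approaching children who undergo a clinically indicated DMSA, so timing may vary, but recruiting a child does not in itself reveal a result.
- *That free scan order shows exposure.* "For Aim 2, there is no specific order for the scans, but they should be performed within six months of each other" concerns scanning. Images can be read later and in any sequence, so a fixed scan order would not mask anyone either.
- *That one reading would decide the 80% hypothesis.* Going from 15/19 (78.9%) to 16/19 (84.2%) crosses 80%, but going from 14/19 (73.7%) to 15/19 does not. The 80% figure is a hypothesis in the background section; the Aim 2 design contrast starts at 60% for sensitivity and 70% for specificity.
- *That the bias would keep the study from stopping at 25%.* No threshold for lack of efficacy is given, so no number of readings maps to that decision.
- *That Aim 1 specificity is affected.* It is not a planned estimate.

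The reverse direction, DMSA classified with the MRI in view, is partly covered because DMSA is a clinical scan and the MRI is not open to providers. The plan still does not say who supplies the study's DMSA classification.

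That this is a pilot with an informal 60% mark lowers the stakes. It does not remove them, since a baseline accuracy estimate is what the pilot is meant to deliver.

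**Conclusion.** The point holds as a gap in conduct. The plan neither separates the readers nor requires the MRI reading to be fixed before DMSA is known, and in Aim 2 it admits children whose DMSA result already exists. Bias, if present, would run upward in Aim 2 sensitivity and specificity and in Aim 1 sensitivity. It rests on few readings: 5.3, 2.2 and 3.2 points each. These sizes assume the planned numbers and the plan's own prevalences of 30% and 90%. The total effect cannot be estimated from the document, and the range over f is illustration only. A reader might infer that the results will be inflated; the text supports only that nothing prevents it. This should be corrected, and the correction is small.

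**What to change.** In Data Collection, Handling, Storage and in the Data and Safety Monitoring Plan:

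1. State by role who makes the study MRI reading and who supplies the DMSA classification.
2. Require one MRI reading per child, recorded and locked before that reader opens the DMSA result, including for children with an earlier DMSA.
3. State that the DMSA classification is made without the quick MRI.
4. Record for each child whether the MRI reader already knew the DMSA result, and report how many did.
5. Use only locked readings in the 25% evaluation and in the final analysis.

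The cost is protocol wording, one extra data field and a little coordinator time. No extra readers or scans are needed, and providers' access to DMSA is unchanged. If MRI readings are already made without DMSA, little beyond the wording and the extra field is needed.

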The Validity of the Quick Renal MRI in Pediatric Kidney Disease

10/11/2023

NCT03959163

TITLE PAGE

Title:

• The Validity of the Quick Renal MRI in Pediatric Kidney Disease

PI Name and Institutional Affiliation:

[name]
 University of Wisconsin School of Medicine and Public Health, Department of Urology

Protocol Version Date:

• October 11, 2023

Co-Investigators

- [name]
 University of Wisconsin School of Medicine and Public Health, Department of Radiology
- [name]
 University of Wisconsin School of Medicine and Public Health, Department of Pediatrics

Funding Sponsor:

None

PROJECT SUMMARY

Children born with congenital anomalies of the urinary tract are susceptible to kidney infections and scarring. They form a high risk group for developing renal insufficiency in adulthood. A basic tenet in pediatric urology is that kidney infections should be prevented and otherwise promptly identified to minimize the risk of acquiring renal scars and permanent tissue damage.

The current radiologic standard for renal infection and scarring is the 99mTechnetium-dimercaptosuccinic acid (99mTc- DMSA) renal scan. This exam requires an intravenous injection, occurs over a 3 hour period, involves exposure to radiation, and can require sedation of young children. We propose a new imaging method that is a rapid, injection-, sedation-, and radiation-free alternative: the quick renal MRI. This proposal hypothesizes that the quick renal MRI has high validity compared to the DMSA scan in the detection of acute renal infections and scars. If the quick renal MRI is accurate, it could potentially replace the DMSA scan for those specific questions and ease the burden of testing for children with chronic renal disease. Findings from these studies will provide preliminary data and rationale for a multi-centered study to further test this new technology.

BACKGROUND AND SIGNIFICANCE

Pyelonephritis: a common serious infection in children.

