Diffusion weighted imaging (DWI) is a method of non-enhanced MRI that has been primarily applied in diagnosing intracranial processes including abscesses. In areas of acute inflammation, water diffusion will be restricted due to a high concentration of inflammatory cells, bacteria, viscosity, and high protein levels. 28 DWI is not standard in the imaging of renal disease but has recently shown promise in imaging pyelonephritis. 29 Compared to the gadolinium-enhanced T1-weighted method, DW MRI has shown good agreement for the diagnosis of pyelonephritis with 95%-100% sensitivity, 93.5%-95% specificity

PI: [name]

and excellent interobserver reproducibility.30-32 DWI may provide a gadolinium - free means of

PI: [name]

evaluation for patients suspected to have pyelonephritis but comparison to the 99mTc- DMSA standard has not yet been undertaken. We hypothesize that the quick renal MRI will have at least 80% sensitivity compared to the 99mTc- DMSA standard in the diagnosis of acute pyelonephritis.

MRI has also shown promise in the detection of renal scars. In 1999, 24 children with neurogenic bladder and a history of UTI underwent conventional MRI and 99mTc- DMSA.33 The T1 fat saturated sequence had 82% concordance with DMSA. Its images were inherently tomographic with the hyperintense renal cortex contrasting with the surrounding hypointense perinephric tissues, allowing the detection of cortical scars which relied on contour contractions. In an independent study with 34 children after their first UTI, MRI had a sensitivity of 77% and specificity of 87%.34 It was agreed that the T1 fat saturated image was the optimum method to detect renal parenchymal defects. To date, the accuracy of a quick renal MRI study compared to DMSA using a single, fat-saturated T1-W sequence for the detection of renal scarring has yet to be established. A rapid, injection- and contrast- free imaging scan would be a novel method for accurate and timely diagnosis of acute pyelonephritis and for surveillance for renal scars in high risk pediatric groups. We hypothesize that the quick renal MRI will have at least 80% sensitivity and specificity compared to the 99mTc- DMSA standard in the diagnosis of renal scars.

SPECIFIC AIMS/REGISTRY OBJECTIVES

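### Aim 1: 34 subjects give about 17–22% (two-sided) or 34–41% (one-sided) power for sensitivity 80% versus 90%, not the stated 80%

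*Combined protocol and SAP*

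**What the plan says.** The Aim 1 paragraph of Statistical Considerations sets its inputs as follows: "With a power of at least 80%, a target significance level of 0.05, and an estimate of 90% prevalence of DMSA confirmed acute pyelonephritis". From these it concludes that "the minimum sample size required to detect a change in sensitivity from 80%-90% is 34 subjects". It names no test, does not say whether the 0.05 is one- or two-sided, and shows no calculation. The same section defines sensitivity as true positives over true positives plus false negatives, so the denominator is the DMSA-positive children only.

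Two other places bear on the point. The Background (Quick MRI) states the Aim 1 hypothesis as the expectation that the quick MRI "will have at least 80% sensitivity compared to the 99mTc- DMSA standard in the diagnosis of acute pyelonephritis", which is the same 80% benchmark. At the end of Statistical Considerations the study is described as a pilot with one numerical rule: "If the preliminary sensitivity/specificity percentages are less than 60%, we would be less enthusiastic about carrying out future research on this question".

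**The concern.** Thirty-one or so informative children is very few for separating two proportions only 10 percentage points apart, so a claim of 80% power needs checking. The sentence is the only support offered for the Aim 1 enrolment target. The Project Summary also says that "Findings from these studies will provide preliminary data and rationale for a multi-centered study". If the power statement is false, the IRB, readers and the planners of that later study would wrongly believe that 34 children can distinguish 90% sensitivity from 80%.

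**Working it through.** **Inputs, all from the Aim 1 paragraph of Statistical Considerations.** Null sensitivity p0 = 0.80; alternative p1 = 0.90; α = 0.05 (sidedness not stated, so both are run); power 0.80; prevalence 0.90; N = 34. That paragraph makes no allowance for dropout, and none is applied.

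**Step 1. Informative children.** 34 × 0.90 = 30.6, so 30 or 31 DMSA-positives.

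**Step 2. Try to reproduce 34 by the normal approximation.** The number of positives needed is n = [(z_α √(p0(1−p0)) + z_β √(p1(1−p1))) / (p1−p0)]², and subjects = n / 0.90.

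- Two-sided: [(1.96 × 0.4 + 0.8416 × 0.3) / 0.1]² = 107.4 positives; 107.4 / 0.9 = 119.4, so 120 subjects.
- One-sided: [(1.645 × 0.4 + 0.8416 × 0.3) / 0.1]² = 82.9 positives; 82.9 / 0.9 = 92.1, so 93 subjects.

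Neither is near 34. Continuity-corrected, null-variance-only, alternative-variance-only and arcsine versions were also tried, one- and two-sided, and so was swapping null and alternative. The smallest N from any version for 80% to 90% is 62 (one-sided, alternative variance only).

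**Step 3. Exact binomial sample size.** Exact power is jagged in n, so two values are given: where it first reaches 0.80, and from where it stays there.

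| | First reaches 80% | Stays at or above 80% |
|---|---|---|
| Two-sided | 107 positives; 107/0.9 = 118.9, so 119 subjects | 113 positives; 113/0.9 = 125.6, so 126 subjects |
| One-sided | 82 positives; 82/0.9 = 91.1, so 92 subjects | 94 positives; 94/0.9 = 104.4, so 105 subjects |

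**Step 4. Exact power at N = 34.** Find the smallest r with P(X ≥ r | n, 0.80) ≤ 0.025 (two-sided) or ≤ 0.05 (one-sided). Power is then P(X ≥ r | n, 0.90).

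| DMSA-positives | Two-sided: r, power | One-sided: r, power |
|---|---|---|
| 30 | 29, 18.4% | 28, 41.1% |
| 31 | 30, 17.0% | 29, 38.9% |
| 34 (all positive) | 32, 32.6% | 32, 32.6% |

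Averaging over Binomial(34, 0.9) for the number of positives gives 18.1% two-sided and 33.8% one-sided. The smallest N with averaged power of at least 80% is 123 two-sided and 99 one-sided.

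The normal approximation, Φ[((p1−p0)√n − z_α √(p0(1−p0))) / √(p1(1−p1))], gives at n = 31:

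- two-sided: Φ[(0.1 × 5.568 − 1.96 × 0.4) / 0.3] = Φ(−0.76) = 22%
- one-sided: Φ[(0.1 × 5.568 − 1.645 × 0.4) / 0.3] = Φ(−0.34) = 37%

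**Step 5. Precision at N = 34 (Clopper–Pearson 95% intervals, 31 positives).** 28/31 = 90%: 74% to 98%. 29/31 = 94%: 79% to 99%. 30/31 = 97%: 83% to 99.9%. Only the last excludes 80%.

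**Step 6. Is this method fair to the plan?** Yes. The exact two-sided test reproduces the Aim 2 figure in the same section. For sensitivity 60% to 90%, 18 positives give 73.4% power and 19 give 88.5%; 19 / 0.30 = 63.3, so 64 subjects, as stated there.

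**Step 7. Where might 34 come from?** There are two candidates, neither confirmed by the documents.

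- A change from 70% to 90%, exact two-sided, needs 31 positives (power 80.7%). But 31 / 0.9 = 34.4, which rounds up to 35, and averaged power at 34 subjects is 73.3%.
- A change from 80% to 95%, exact one-sided, needs 30 positives; 30 / 0.9 = 33.3, so 34.

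**Step 8. The 60% rule.** With true sensitivity 90%, the chance that 18 or fewer of 31 are detected (a point estimate below 60%) is about 0.000004. The rule is unaffected by the power error.

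**The case against.** There are three serious replies.

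First, this is a pilot. The Specific Aims word Aim 1 as feasibility, the planned analysis is a simple proportion with no test, and the only numerical rule is at 60%. All of that is true, and it limits the damage. It does not withdraw the claim of at least 80% power. The same section says Aim 1 will determine sensitivity, and the Background sets 80% as the benchmark.

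Second, the printed 80% may be a slip for 70%, since the method that reproduces Aim 2 comes close to 34 for 70% to 90%. That is plausible but remains an inference. It requires 34.4 to be rounded down where Aim 2 rounded 63.3 up, and it conflicts with the Background's own 80% hypothesis. If it is right, the printed sentence is still wrong.

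Third, with the test unstated, the power ranges depend on the method. This stands in part. The arcsine approximation gives 34–35% two-sided and 46–47% one-sided, and the most favourable approximation (alternative variance only, one-sided) gives 58% at 31 positives. None approaches 80%.

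**Conclusion.** The concern holds: the Aim 1 sample-size statement is wrong for the inputs it lists. By exact and standard normal calculations, power at 34 subjects is about 17–22% two-sided or 34–41% one-sided. The number needed is roughly 3.5 times the stated figure two-sided (119/34 = 3.5) and 2.7 times one-sided (92/34 = 2.7), taking the smallest exact values. This rests on a one-sample binomial comparison of 80% with 90% among DMSA-positive children, α = 0.05, 90% prevalence and no dropout; any dropout would lower power further. The statement must be corrected because it is the sole justification for the target. The correction concerns what the plan claims; it does not undermine a pilot of this size or the 60% rule.

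**What to change.** Keep 34 subjects, remove the claim of at least 80% power for 80% to 90%, and justify the number by pilot precision. Suggested text:

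> The Aim 1 target of 34 subjects (about 31 DMSA-positive at 90% prevalence) is set for a pilot estimate of sensitivity, reported with an exact 95% confidence interval. If 28 of 31 DMSA-positive children are detected (90%), the interval is 74% to 98%, which does not exclude 80%. Power to show sensitivity above 80% when the true value is 90% is about 18% (two-sided exact, alpha 0.05) or 34% (one-sided exact), averaged over the number of DMSA-positive children.

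This wording is true whatever the origin of 34. The sponsor should also look for the source calculation. If a different change in sensitivity was intended, that input, the test, its sidedness and N need to be reconciled and stated before any power claim is restored.

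The cost is three sentences in place of one. No patients are added, and the 80% hypothesis and the 60% rule stay as they are. The plan gives up its claim that Aim 1 is powered to separate 90% from 80%.
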